3.8. Contraindications

Based on the immune-stimulatory mechanism of action of JTX-2011, it should not be administered to subjects with any of the following:

- History of intolerance, hypersensitivity, formation of anti-drug antibodies, or severe immune-related adverse events to prior immunotherapies, including CTLA-4 inhibitors, PD-1 inhibitors, or immune agonists. Subjects who discontinued prior immunotherapies for immune-related adverse events that are well-controlled with appropriate treatment, and, in the opinion of the investigator, should not prevent the subject from receiving study drug, may be enrolled if approved by the medical monitor;
- Active disease requiring systemic immunosuppressive therapy;
- Any known primary or acquired diagnosis of immunodeficiency, or treatment with systemic steroids or any other form of immunosuppressive therapy within 7 days prior to CID1. Exception: inhaled or topical steroids and adrenal replacement doses are permitted in the absence of active autoimmune disease;
- Known severe intolerance to or life-threatening hypersensitivity reactions to humanized monoclonal antibodies or intravenous immunoglobulin preparations; any history of anaphylaxis; prior history of human anti-human antibody response; known allergy to any of the study medications, their analogues, or excipients in the various formulations of any agent.

3.8.1. Concomitant Medications

Documentation of concomitant medication use will be recorded at each visit.

3.8.1.1. Prohibited Concomitant Medications/Therapies

Immune-suppressive steroids or any other form of immunosuppressive therapy within 7 days prior to CID1

3.8.1.2. Allowed Concomitant Medications

- Inhaled, topical or oral steroids and adrenal replacement doses are permitted.

- Palliative radiation to non-target lesions only is allowed during study treatment in consultation with the medical monitor.
- One-time dose of immunosuppressive agents used prophylactically for contrast allergies

4. SELECTION OF STUDY POPULATION

4.1. Inclusion Criteria

All subjects must meet the following inclusion criteria to be eligible for study participation:

- 1) Must be willing and able to participate and comply with all trial requirements and able to provide signed and dated informed consent prior to initiation of any trial procedures;
- 2) **All Parts:**
 - a) Evaluable or measurable disease, according to RECIST v1.1 criteria, with at least one measurable lesion (except for Parts A, B, E and G, see below);
 - b) Meets the requirements for the intended study cohort.
- 3) **Parts A, B and E Dose Escalation:**

Any advanced and/or refractory, non-hematological, extracranial malignancy with disease progression after treatment with all available therapies known to confer clinical benefit. Subjects enrolled to dose escalation cohorts may have evaluable but non-measurable disease.
- 4) **Parts A and B Safety/PK/PD Expansion Cohorts (AP1, AP2, BP1, and BP2):**
 - a) Any advanced and/or refractory, non-hematological, extracranial malignancy with disease progression after treatment with all available therapies known to confer clinical benefit, with ≥ 1 ICOS expression levels as determined by immunohistochemistry on archival tumor or history of documented PD-L1 expression;
 - b) Must have a tumor lesion that can be biopsied at acceptable risk and must agree to both a fresh biopsy between screening and CID1 and a second biopsy after completion of 2 cycles of study treatment.
- 5) **Part C** – all subjects must have progressed on or after all approved therapies. If prior therapy included a PD-1 inhibitor, subjects must have progressed after at least 2 months of this therapy:
 - a) C01: HNSCC;
 - b) C02: NSCLC;
 - c) C03: Any advanced, non-hematological, extracranial malignancy other than those eligible for C01, C02, C04, or C05 (*closed to enrollment*);
 - d) C04 and C64: Gastric or gastroesophageal junction adenocarcinoma, including adenocarcinoma of the lower esophagus. Subjects with HER2 over-expressing tumors must have progressed on or after FDA approved therapy for HER2 over-expressing metastatic gastric or gastroesophageal junction adenocarcinoma;
 - e) C05: Endometrial cancer that is locally determined to have a mismatch repair deficiency (dMMR) as determined by immunohistochemical complete loss of expression (absence of nuclear immunoreactivity) of at least one of the mismatch repair genes MSH2, MSH6, MLH1 and PMS2, or to be microsatellite instability-high (MSI-H) by polymerase chain reaction (PCR) (*closed to enrollment*);

- f) C06: TNBC that is immunotherapy naïve [negative per ASCO/CAP guidelines for estrogen receptor (ER) protein expression and progesterone receptor (PR) protein expression (< 1% of tumor cell nuclei are immunoreactive), and negative for human epidermal growth factor receptor (HER2) protein expression by IHC assay (0 or 1) or by fluorescence *in situ* hybridization (FISH)];
- g) C07: Mesothelioma that is immunotherapy naïve;

6) Part D:

- a) D01: HNSCC that progressed on or after at least 2 months of a prior PD-1 inhibitor;
- b) D02: NSCLC that progressed on or after at least 2 months of a prior PD-1 inhibitor; Subjects with EGFR or ALK genomic tumor aberrations must have progressed on or after FDA approved therapy for these aberrations;
- c) D03: TNBC [negative per ASCO/CAP guidelines for estrogen receptor (ER) protein expression and progesterone receptor (PR) protein expression (< 1% of tumor cell nuclei are immunoreactive), and negative for HER2 protein expression by IHC assay (0 or 1+) or by FISH];
- d) D04: Melanoma that progressed on or after at least 2 months of a prior PD-1 inhibitor (*closed to enrollment*);
- e) D05: gastric cancer, including subjects with cancer of the gastro-esophageal (G-E) junction. Subjects with HER2 over-expressing tumors must have progressed on or after FDA approved therapy for HER2 over-expressing metastatic gastric or gastroesophageal junction adenocarcinoma;
- f) D06: Endometrial cancer that is locally determined to have a dMMR as determined by IHC complete loss of expression (absence of nuclear immunoreactivity) of at least 1 of the mismatch repair genes MSH2, MSH6, MLH1 and PMS2, or to be MSI-H by PCR (*closed to enrollment*);
- g) If a PD-1 or PD-L1 inhibitor is approved for treatment of TNBC during enrollment of this study, eligibility for subjects within that indication will require progression during or after prior treatment with the approved PD-1 or PD-L1 inhibitor;

7) Part F:

- a) F61: mCRPC that has progressed on or after treatment with at least 1 prior standard of care therapy;
- b) F62: Unresectable or metastatic melanoma with ≤ 2 prior lines of therapy in the unresectable or metastatic setting;

8) Part G:

- a) Recurrent or metastatic HNSCC previously treated with with disease progression on or after platinum-containing chemotherapy;

- b) Metastatic NSCLC that has high PD-L1 expression (TPS \geq 50%) as determined by an FDA-approved test, with no EGFR or ALK genomic tumor aberrations;
 - c) Recurrent or metastatic gastric or gastroesophageal junction adenocarcinoma or adenocarcinoma of the lower esophagus with disease progression on or after one prior line of therapy, including HER2/neu-targeted therapy, if appropriate;
 - d) Recurrent or metastatic MSI-H solid tumors that have progressed on prior FDA-approved treatment and who have no satisfactory alternative treatment options or MSI-H colorectal cancer that has progressed following treatment with a fluoropyrimidine, oxaliplatin and irinotecan;
 - e) Any advanced and/or refractory, non-hematological, extracranial malignancy with disease progression after treatment with all available therapies known to confer clinical benefit.
- 9) **Part H** – all subjects must be immunotherapy naive:
- a) H31: Recurrent or metastatic HNSCC with disease progression on or after platinum-containing chemotherapy;
 - b) H32: Metastatic NSCLC that has high PD-L1 expression (TPS \geq 50%), as determined by an FDA-approved test, with no EGFR or ALK genomic tumor aberrations;
 - c) H33: metastatic or recurrent TNBC [negative per ASCO/CAP guidelines for ER protein expression and PR protein expression (< 1% of tumor cell nuclei are immunoreactive), and negative for HER2 protein expression by IHC assay (0 or 1) or by FISH] with \leq 1 prior line of therapy in the metastatic or recurrent setting;
 - d) H34 and H64: Recurrent locally advanced or metastatic gastric or gastroesophageal junction adenocarcinoma including adenocarcinoma of the lower esophagus with disease progression on or after 1 prior line of therapy, including HER2/neu-targeted therapy, if appropriate;
 - e) H35: Unresectable or metastatic MSI-H solid tumors that have progressed on prior FDA-approved treatment and who have no satisfactory alternative treatment options or MSI-H colorectal cancer that has progressed following treatment with a fluoropyrimidine, oxaliplatin, and irinotecan;
- 10) Male or Female \geq 18 years of age;
- 11) Have an ECOG performance status 0-1. Subjects with ECOG 2 may be considered for enrollment in Parts C, D, F and H if approved by medical monitor;
- 12) Have a predicted life expectancy of \geq 3 months;
- 13) Have the following laboratory values:
- a) Serum creatinine $< 2 \times$ ULN
 - b) Total bilirubin \leq ULN unless prior history of Gilbert's syndrome;
 - c) Aspartate transaminase and alanine transaminase $\leq 2.5 \times$ ULN;
 - d) Hemoglobin ≥ 9.0 g/dL;
 - e) Platelets $\geq 75 \times 10^9$ cells/L;

- f) Absolute neutrophil count $\geq 1.5 \times 10^9$ cells/L (without the use of hematopoietic growth factors). Subjects with lower ANC may be enrolled if not the result of prior therapy, if approved by medical monitor;
 - g) Serum albumin $\geq 75\%$ of LLN;
- 14) If medical history of the following, case should be reviewed with the Medical Monitor:
- a) Prior biliary tract disorders (as based on Hepatobiliary SOC high level terms of: obstructive bile duct disorders, hepatic vascular disorders, structural and other bile duct disorders)
 - b) Portal hypertension and/or hepatic vascular disorders
- 15) Women of child-bearing potential (WOCBP) must have a negative serum pregnancy test at screening and a negative urine pregnancy test prior to administration of each dose of JTX-2011;
- 16) WOCBP and males with partners of child-bearing potential must agree to use adequate birth control throughout their participation and for 5 months following the last study treatment.

4.2. Exclusion Criteria

A subject with any one of the following criteria will not be eligible for study participation:

- 1) Receiving concurrent anti-cancer treatment (excluding radiation therapy, either approved or investigational; please see Section 3.8.1.1);
- 2) Have refused standard therapy;
- 3) Have received anti-cancer therapies listed below within the specified timeframe, or who have ongoing toxicity from prior therapy $>$ Grade 1 according to the Common Terminology for Adverse Events (CTCAE). Exceptions to this are: $>$ Grade 1 toxicities which in the opinion of the Investigator should not exclude the patient (e.g. alopecia, Grade 2 neuropathy, hypo- or hyperthyroidism or other endocrinopathies that are well-controlled with hormone replacement) and are approved by the Medical Monitor.
 - a) Have received biologic therapy, including immunotherapy, $<$ 28 days prior to C1D1;
 - b) Have received a CAR-T therapy;
 - c) Have received chemotherapy $<$ 21 days prior to C1D1, or $<$ 42 days for mitomycin or nitrosoureas;
 - d) Have received targeted small molecule therapy $<$ 14 days prior to C1D1;
 - e) Have undergone organ transplantation including allogeneic or autologous stem-cell transplantation, at any time;
- 4) Have undergone a major surgery (excluding minor procedures, e.g. placement of vascular access, biopsy, etc.) $<$ 6 weeks prior to the first day of study treatment, C1D1;

- 5) Have a history of intolerance, hypersensitivity, or treatment discontinuation due to severe immune adverse events on prior immunotherapy, or documented presence of neutralizing anti-drug antibody to nivolumab (Parts B and D), ipilimumab (Part E and F), or pembrolizumab (Parts G and H). Subjects who discontinued prior immunotherapies for immune-related adverse events that are well-controlled with appropriate treatment may be enrolled if approved by the Medical Monitor;
- 6) Have a diagnosis of immunodeficiency, either primary or acquired, or treatment with systemic steroids or any other form of immunosuppressive therapy within 7 days prior to CID1. Exception: inhaled or topical steroids and adrenal replacement doses are permitted in the absence of active autoimmune disease as well as a one-time dose of immunosuppressive agents used prophylactically for contrast allergies;
- 7) Have any active disease requiring systemic immunosuppressive treatment;
- 8) Have known severe intolerance to or life-threatening hypersensitivity reactions to humanized monoclonal antibodies or intravenous immunoglobulin preparations; any history of anaphylaxis; prior history of human anti-human antibody response; known allergy to any of the study medications, their analogues, or excipients in the various formulations of any agent;
- 9) Are symptomatic or have uncontrolled brain metastases, leptomeningeal disease, or spinal cord compression not definitively treated with surgery or radiation (brain metastases that are stable and asymptomatic, either treated or untreated, will be allowed);
- 10) Have current second malignancy at other sites, which requires treatment, or in the judgement of the Investigator, may require treatment within the next year. Concurrent malignancies that do not require treatment and are clinically stable are allowed. A past history of other malignancies is allowed as long as the subject is not receiving specific treatment other than hormonal therapy, and, in the judgement of the Investigator, is unlikely to have a recurrence;
- 11) Have active and clinically relevant bacterial, fungal, or viral infection, including known Hepatitis A, B, or C or HIV (testing not required);
- 12) Have received live vaccines within past 30 days (inactivated vaccines are allowed; seasonal vaccines should be up to date prior to first infusion day);
- 13) Women who are pregnant or breastfeeding;
- 14) Have experienced symptomatic cardiac disease that is unresponsive to surgical or medical management;
- 15) Have any medical or social condition that, in the opinion of the Investigator, might place a subject at increased risk, affect compliance, or confound safety or other clinical trial data interpretation.

4.3. Reproductive Restrictions

[figure not shown]
There are no data regarding the effect of JTX-2011 on the unborn fetus. JTX-2011 should not be administered to pregnant women. Embryo-fetal toxicity is a labeled warning for nivolumab, ipilimumab, and pembrolizumab (Opdivo® Full Prescribing Information {Bristol-Myers Squibb Company 2017a}), Yervoy® Full Prescribing Information {Bristol-Myers Squibb Company

2017b), Keytruda® Full Prescribing Information {Merck & Co Inc 2017}). Women of child-bearing potential (WOCBP) must have a negative serum pregnancy test during screening period and a negative urine pregnancy test prior to administration of each dose of JTX-2011 throughout the study. Women of childbearing potential and males with partners of child-bearing potential must agree to use adequate birth control throughout their participation and for 5 months following the last study treatment.

5. STUDY DESIGN

This is a Phase 1/2, open label, multicenter, first-in-human trial to evaluate the safety and tolerability, PK, pharmacodynamics, and preliminary efficacy of the ICOS agonist monoclonal antibody JTX-2011 alone and in combination with nivolumab, ipilimumab, or pembrolizumab in adult subjects with advanced and/or refractory solid tumor malignancies. The study will be conducted at approximately 36 sites in North America. The study is divided into 8 parts; Part A, Part B, Part C, Part D, Part E, Part F, Part G, and Part H. Subjects may be enrolled into any open cohorts for which they qualify at the discretion of the Investigator.

Figure 5: JTX-2011-101 Study Schema

Abbreviations: dMMR=mismatch repair deficient; HNSCC=head and neck squamous cell carcinoma; PK=pharmacokinetics; PD=pharmacodynamics; mCRPC=metastatic castration-resistant prostate cancer; MSI-H= microsatellite instability-high; NSCLC=non-small cell lung cancer; TNBC=triple-negative breast cancer.

Approximately 498 evaluable subjects will be enrolled, assuming the following:

5.1. Part A (JTX-2011 Monotherapy Dose Escalation) – Completed Enrollment

Part A comprises escalating doses of JTX-2011 administered intravenously (IV) once every 3 weeks in consecutive cohorts, plus Safety/PK/PD Expansion Cohorts (AP1 and AP2) at each of two or more dose levels. A total of 27 subjects were enrolled across six (6) dose levels. An additional 12 subjects were enrolled in the safety and PK/PD data (Safety/PK/PD Expansion Cohorts AP1 and AP2). Archival tumor tissue will be collected on all dose escalation subjects for retrospective assessment of ICOS and PD-L1 expression. Subjects enrolled in AP1 and AP2 will be required to have ≥ 1 ICOS expression levels as determined by IHC on archival tumor tissue or history of documented PD-L1 expression as well as fresh tumor biopsies prior to CID1 and after two cycles of study treatment for assessment of potential predictive biomarkers and to assess changes in T cell subsets and gene expression after treatment with JTX-2011. A minimal level of ICOS or PD-L1 expression implies the presence of T cells in the tumor, which is required for evaluation of changes in T cell subsets after treatment.

5.2. Part B (JTX-2011 in Combination with Nivolumab Dose Escalation) – Completed Enrollment

Part B comprises escalating doses of JTX-2011 in combination with nivolumab (both agents administered IV once every 3 weeks) in consecutive cohorts, plus Safety/PK/PD Expansion Cohorts (BP1 and BP2) at each of two or more dose levels. A total of 16 subjects were enrolled across four (4) dose levels. An additional 15 subjects were enrolled in the safety and PK/PD data (Safety/PK/PD Expansion Cohorts BP1 and BP2). Archival tumor tissue will be collected on all dose escalation subjects for retrospective assessment of ICOS and PD-L1 expression. Subjects enrolled in BP1 and BP2 will be required to have ≥ 1 ICOS expression levels as determined by IHC on archival tumor tissue or history of documented PD-L1 expression as well as fresh tumor biopsies prior to CID1 and after two cycles of study treatment for assessment of potential predictive biomarkers and to assess changes in T cell subsets and gene expression after treatment with JTX-2011. A minimal level of ICOS or PD-L1 expression implies the presence of T cells in the tumor, which are required for evaluation of changes in T cell subsets after treatment.

5.3. Part E (JTX-2011 in Combination with Ipilimumab Dose Escalation)

Part E comprises escalating doses of JTX-2011 in combination with ipilimumab in consecutive cohorts (JTX-2011 will be administered IV q6w and will be administered until a subject meets criteria for discontinuation; ipilimumab will be administered IV q3w for up to 4 doses).

Three (3) dose escalation cohorts are planned at doses of 0.03 mg/kg, 0.1 mg/kg, and 0.3 mg/kg (approximately 3 dose levels with a minimum of 3 or up to 6 subjects per dose level, exclusive of replacement subjects and evaluation of escalation dose levels [approximately 18 subjects]). A dose de-escalation cohort of 0.01 mg/kg of JTX-2011 may be explored.

Table 3: Part E Dose Escalation Schema

Cohort	JTX-2011 Dose
E63	0.3 mg/kg
E62	0.1 mg/kg
E61*	0.03 mg/kg
E60	0.01 mg/kg

* Starting dose level

5.4. Part G (JTX-2011 in Combination with Pembrolizumab Combination Dose Escalation)

Part G comprises JTX-2011 in combination with pembrolizumab in consecutive cohorts (both agents administered IV q3w until a subject meets criteria for discontinuation).

Two (2) dose escalation cohorts are planned at doses of 0.1 mg/kg and 0.3 mg/kg (approximately 2 dose levels with a minimum of 3 or up to 6 subjects per dose level, exclusive of replacement subjects and evaluation of escalation dose levels [approximately 12 subjects]). A dose de-escalation cohort of 0.03 mg/kg of JTX-2011 may be explored.

Subjects in Part G are required to have a fresh tumor biopsy during screening. In situations where archival tissue is not available or biopsies are not feasible (e.g., would expose the subject to unreasonable health risks), one or more of these requirements may be waived after discussion with the Medical Monitor.

Table 4: Part G Dose Escalation Schema

Cohort	JTX-2011 Dose
G32	0.3 mg/kg
G31*	0.1 mg/kg
G30	0.03 mg/kg

* Starting dose level

5.5. Part C (JTX-2011 Monotherapy Phase 2)

Part C will include approximately 15 subjects in each of 8 dose cohorts (total of 120 subjects) in the indications listed below at 0.3 mg/kg in both the q3w and q6w dosing schedule. All subjects must have progressed on or after all approved therapies. If prior therapy included a PD-1 inhibitor, subjects must have progressed after at least 2 months of this therapy:

q3w JTX-2011 dosing

- C01: HNSCC;
- C02: NSCLC;
- C03: Any tumor type other than those eligible for C01, C02, C04, or C05 (*closed to enrollment*);
- C04: Gastric cancer or gastroesophageal junction adenocarcinoma;
- C05: MSI-H or dMMR endometrial cancer (*closed to enrollment*);

- C06: TNBC that is immunotherapy naïve;
- C07: Mesothelioma that is immunotherapy naïve.

q6w JTX-2011 dosing

- C64: Gastric cancer or gastroesophageal junction adenocarcinoma

Pre-screening for ICOS will not be required. Subjects in Part C are required to have archival tumor and two fresh tumor biopsies (one during screening and one post-dose between C2D1 and C3D1 for subjects on the q3w, or between C2D1 and C2D22 for subjects on the q6w). In situations where archival tissue is not available or biopsies are not feasible (e.g., would expose the subject to unreasonable health risks), one or more of these requirements may be waived after discussion with the Medical Monitor.

To complete enrollment in the HNSCC (C01), NSCLC (C02), gastric (C04 and C64), and TNBC (C06), at least 15 assessable pre-treatment fresh biopsies must have been obtained in each cohort, 10 of which must have an ICOS score ≥ 2 . To complete enrollment in the mesothelioma cohort (C07), 10 subjects must have enrolled with ICOS ≥ 2 based on archival tissue, rather than fresh tissue.

If a subject has progressed in Part C, nivolumab can be added to the subject’s treatment regimen after confirmation of progression and at the discretion of the Sponsor and investigator. After the completion of Part G, instead of nivolumab, pembrolizumab can be added to the subject’s treatment regimen upon confirmation of progression and at the discretion of the Sponsor and investigator. Confirmatory scans may be performed no less than 4 weeks from the most recent radiographic assessment documenting disease progression.

Figure 6: Part C q3w Treatment Schema

[figure not shown]
[figure not shown]

Figure 7: Part C q6w Treatment Schema

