	
 Examine changes from baseline in gene signatures and immune cell subsets within tumor biopsies after treatment with JTX-2011 monotherapy (Part C) and JTX-2011 in combination with ipilimumab (Part F).
Study Drugs:	
 JTX-2011 is a humanized IgG1κ monoclonal antibody that is an agonist of Inducible CO-Stimulator of T cells (ICOS). Nivolumab, marketed as Opdivo[®], is a human IgG4κ anti-PD-1 monoclonal antibody manufactured by Bristol-Myers Squibb. Ipilimumab, marketed as Yervoy[®], is a human IgG1κ cytotoxic T-lymphocyte antigen 4 (CTLA-4)-blocking antibody manufactured by Bristol-Myers Squibb. Pembrolizumab, marketed as Keytruda[®], is a humanized IgG4κ anti-PD-1 monoclonal antibody manufactured by Merck.
Number of Subjects:	
Approximately 498 evaluable subjects will be enrolled, assuming the following:
 
 Part A: A total of 27 subjects were enrolled across six (6) dose levels. An additional 12 subjects were enrolled in the safety and PK/PD data (Safety/PK/PD Expansion Cohorts AP1 and AP2); Part B: A total of 16 subjects were enrolled across four (4) dose levels. An additional 15 subjects were enrolled in the safety and PK/PD data (Safety/PK/PD Expansion Cohorts BP1 and BP2); Part C: Approximately fifteen (15) subjects each in cohorts C01-C07 and C64 (approximately 120 subjects); Part D: Approximately fifteen (15) subjects each in cohorts D01-D06 (approximately 90 subjects). Part E: Approximately three (3) dose levels with a minimum of 3 or up to 6 subjects per dose level, exclusive of replacement subjects and evaluation of escalation dose levels (approximately 18 subjects); Part F: Approximately fifteen (15) subjects each in cohorts F61-F62 (approximately 30 subjects); Part G: Two (2) dose levels with a minimum of 3 or up to 6 subjects, exclusive of replacement subjects and evaluation of escalation dose levels (approximately 12 subjects); Part H: Approximately fifteen (15) subjects each in cohorts H31, H32, H33, and H35 (approximately 60 subjects) and approximately 49 subjects each in cohorts H34 and H64 (approximately 98 subjects).
Number of Centers:	Approximately 36 sites in North America

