Further analysis conducted within Jounce Therapeutics has strengthened the rationale for exploration of JTX-2011 in gastric cancer. Gastric cancer as a whole exhibits an ICOS score of 2 or higher by IHC in approximately 28% of tumors tested. Exploration of ICOS expression within gastric cancer via an orthogonal RNAseq dataset (The Cancer Genome Atlas [TCGA] “STAD [stomach adenocarcinoma]”), indicates that the frequency of ICOS expression varies with respect to molecular subtype {Cancer Genome Atlas Research 2014} with the highest frequency of medium and high ICOS levels seen in microsatellite-instability high (MSI-H) and Epstein-Barr virus positive subsets. These subsets represent approximately 8-9.4% and 4-10%, respectively, of all gastric cancers {Boger 2016; Iizasa 2012; Kim 2016}, and are mutually exclusive.

MSI-H tumors in general are of particular interest, as mismatch repair deficiency is associated with a deficiency in the DNA repair pathways in a certain fraction of human tumors. These mismatch repair deficient, microsatellite instable (MSI) tumors accumulate 10-100 fold more mutations in the tumors as compared to the microsatellite stable counterparts {Cancer Genome Atlas Research 2014}. A MSI-H tumor may display more non-self or neo-antigens to the surrounding tumor microenvironment, and therefore be immunologically recognized as foreign. These non-self antigens may attract cells of the immune system such that they infiltrate the tumor. Thus as a consequence of a higher number of mutations, MSI-H tumors tend to have higher levels of infiltrate than those that are microsatellite stable (MSS) {Jass 1998}. MSI-H tumors, therefore, may be more likely to respond to immunotherapy {Le 2015}, as reflected by FDA approvals for nivolumab marketed as Opdivo in MSI-H colorectal cancer and Pembrolizumab, marketed as Keytruda® in MSI-H solid tumors regardless of tissue of origin (Opdivo® Full Prescribing Information {Bristol-Myers Squibb Company 2017a}, Keytruda® Full Prescribing Information {Merck & Co Inc 2017}).

Another example of an MSI-H tumor is endometrial cancers. Endometrial cancers also exhibit a population of MSI-H tumors that are known to be highly infiltrated. In a cohort of endometrial cancer patients, MSI status was determined by the presence or absence of mismatched repair genes (MLH1, MSH2, PMS2, MSH6) according to established guidelines {Egoavil 2013} at

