6.9. Pre-Screening for ICOS Expression

Subjects who have archival biopsy samples available for submission to the central lab for measurement of ICOS expression may provide informed consent for submission of archival samples for evaluation prior to undergoing the informed consent process and screening for full study participation. A separate abbreviated Informed Consent Form will be provided to sites to utilize for this purpose upon approval by their governing IRB. In situations where a subject's archival samples are completely exhausted, subjects may elect to have a biopsy performed per institutional guidelines to serve as an archival sample. Results from ICOS testing of archival tissue performed prior to the 28-day screening window will not need to be repeated.

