9.4.1. Determination of Sample Size

For Part A, Part B, Part E, and Part G, the choice of the number of subjects is based on the classical 3 + 3 design. The approximate sample size in the dose escalation cohorts in Part A will be 36 evaluable subjects assuming that 6 subjects are assigned at each of 6 planned dose levels. The approximate sample size of the dose escalation cohorts in Part B will be 24 evaluable subjects assuming that 6 subjects are assigned at each of 4 planned dose levels. The approximate sample size of the dose escalation cohorts in Part E will be 18 evaluable subjects assuming that 6 subjects are assigned at each of 3 planned dose levels. The approximate sample size of the dose escalation cohorts in Part G will be 12 evaluable subjects assuming that 6 subjects are assigned at each of 2 planned dose levels.

Approximately 8 additional subjects will be enrolled in safety/PK/PD expansion cohorts at each of 2 or more dose levels in Parts A (AP1, AP2) and B (BP1, BP2) to obtain additional safety and PK/PD data. Subjects may also be added if exploration of intermediate dose level(s) of JTX-2011 is warranted or if the SMC recommends adding additional subjects at a given dose level to further understand and clarify safety issues.

Approximately 120 subjects may be enrolled in Part C (approximately 15 in each cohort). Approximately 90 subjects may be enrolled in Part D (approximately 15 subjects per cohort). Approximately 30 subjects may be enrolled in Part F (approximately 15 subjects per cohort). Approximately 15 subjects may be enrolled in each Part H (assuming 3-6 will be enrolled in Part G). For Part C, Part D, Part F, and Part H, a group sequential design will be used to evaluate the preliminary efficacy of JTX-2011 or JTX-2011 in combination with nivolumab, ipilimumab or pembrolizumab, with an interim look for futility.

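### At the protocol's own 28% gastric ICOS prevalence, the completion rule for C04 and C64 implies about 36 subjects per cohort on average, not the stated 15, and no rule in Part C limits ICOS-low enrolment

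*Protocol*

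**What the plan says.** Size. Protocol section 5.5 states: "Part C will include approximately 15 subjects in each of 8 dose cohorts (total of 120 subjects"). The Synopsis (Number of Subjects) has "Approximately fifteen (15) subjects each in cohorts C01-C07 and C64 (approximately 120 subjects"), and section 9.4.1 has "Approximately 120 subjects may be enrolled in Part C (approximately 15 in each cohort"). SAP section 5 carries the same figures.

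Completion rule. For C01, C02, C04, C64 and C06, section 5.5 requires that "at least 15 assessable pre-treatment fresh biopsies must have been obtained in each cohort, 10 of which must have an ICOS score" of 2 or more. Fifteen is therefore a floor on assessable biopsies, and ten is a quota within them.

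Entry. The same section says "Pre-screening for ICOS will not be required". The C04 and C64 criteria in section 4.1 contain no ICOS condition. Section 6.9 leaves a voluntary route open: subjects with archival tissue "may provide informed consent for submission of archival samples for evaluation prior to undergoing the informed consent process" for the full study.

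Prevalence. Section 1.3 gives the only gastric figure: "Gastric cancer as a whole exhibits an ICOS score of 2 or higher by IHC in approximately 28% of tumors tested".

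Stratification. Protocol section 2.2.1 describes the Part C groups as stratified for ICOS on the fresh biopsy, and SAP section 4 names C04 among the stratified cohorts. Neither gives a cap, slot limit or allocation rule for ICOS-low subjects.

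Part D by contrast. Protocol section 5.6 allows a cohort to grow past 15 so that it contains ten ICOS-high subjects. Section 5.5 has no such sentence.

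**The concern.** A quota of ten ICOS-high subjects within about 15 means that two thirds of the cohort must be ICOS-high. The protocol expects a little over a quarter of gastric tumours to be so. With entry open to all ICOS levels, enrolment would have to run well past 15 before the tenth ICOS-high biopsy appeared.

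Two outcomes are possible as the text stands. The cohorts may grow to more than twice their stated size, with most subjects ICOS-low and receiving monotherapy after their approved treatments have failed. Or they may close without meeting their own completion rule. In either case, sites, review boards and the safety committee have been given a planned size that does not follow from the design.

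**Working it through.** **1. The plan's own totals.** 8 cohorts × 15 = 120 for Part C. All parts: 27 + 12 + 16 + 15 + 120 + 90 + 18 + 30 + 12 + 60 + 98 = 498. Both reproduce, so the addition is sound. The question is whether 15 is the right entry for C04 and C64.

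**2. Inputs.** Quota r = 10 and biopsy floor 15 (section 5.5). Prevalence p = 0.28 (section 1.3). Working assumptions: subjects enter without regard to ICOS, every subject has an assessable fresh biopsy, and results are independent.

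**3. Chance that 15 subjects suffice.** Expected ICOS-high in 15 is 15 × 0.28 = 4.2. With X binomial(15, 0.28), P(X ≥ 10) = 0.0021, about 0.2%. For 15 subjects to contain ten on average, p would have to be 10/15 = 0.667.

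**4. Enrolment to the tenth ICOS-high subject.** This is negative binomial.
- Mean r/p = 10/0.28 = 35.7. The floor of 15 does not change this at the precision shown.
- SD √(r(1 − p))/p = √7.2/0.28 = 9.6.
- Median 35; 10th to 90th percentile 24 to 48; 5th to 95th percentile 22 to 53.
- On average 35.7 − 10 = 25.7, about 26, of those enrolled would be ICOS-low.

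| Subjects enrolled | Probability that the quota is met |
|---|---|
| 15 | 0.2% |
| 20 | 3% |
| 25 | 13% |
| 30 | 32% |
| 36 | 57% |
| 40 | 72% |
| 49 | 91% |

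A 90% chance needs about 48.

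**5. Sensitivity to prevalence.** All values other than 28% are assumed, because the documents give no rate for fresh biopsies in this population.

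| Prevalence | P(at least 10 of 15) | Expected enrolment |
|---|---|---|
| 20% | 0.01% | 50 |
| 25% | 0.08% | 40 |
| 28% | 0.2% | 36 |
| 35% | 1.2% | 29 |
| 40% | 3.4% | 25 |
| 50% | 15% | 20 |
| 60% | 40% | 17 |

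**6. Biopsy waivers.** Section 5.5 allows them, and they can only raise the number. If 90% or 80% of subjects have an assessable biopsy (assumed), the mean becomes 35.7/0.9 = 39.7 or 35.7/0.8 = 44.6.

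**7. Effect on the totals.** Two gastric cohorts: 2 × 35.7 = 71.4 against 30 stated, a difference of 41.4. For C04 alone the difference is 35.7 − 15 = 20.7.

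**The case against.** The strongest defence is stratification. Protocol section 2.2.1 and SAP section 4 both describe it, section 7.1 places the fresh biopsy in screening before the first dose, and section 1.3 says that scores are returned to sites. If ICOS-low places were limited after the screening biopsy, about 36 could be the number biopsied, with the number treated nearer 15. Optional archival testing under section 6.9 could also lead sites to enrich informally. This stands to the extent that a reader cannot rule it out. It does not remove the conflict, because no section says how ICOS-low entry to Part C is limited. Where the protocol does want ICOS to govern entry, as in the safety/PK/PD expansion cohorts (section 4.1, item 4), it makes expression part of an eligibility criterion.

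Second, 28% describes gastric tumours as a whole. Part C takes heavily pretreated patients, some after a PD-1 inhibitor, and section 1.3 reports ICOS upregulation after such agents. The on-study rate could be higher. That also stands and is why the range runs to 50%, but even there 15 subjects would meet the quota only about 15% of the time.

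Third, the sizes are given as approximate, and growth to about 49 (Synopsis) or 76 (section 9.3) is foreseen. Approximate wording covers a modest overrun, not a factor of 35.7/15 = 2.4. The larger sizes depend on the futility look, not on the ICOS quota.

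Fourth, the SAP describes Part C as C01 to C05 only, so C64 may carry less weight in the analysis. C04 alone still shows the conflict.

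**Conclusion.** The stated size of about 15 does not follow from the completion rule for C04 and C64. Under unselected enrolment at 28%, the rule is met with 15 subjects about 0.2% of the time, and expected enrolment is about 36 per cohort (10th to 90th percentile 24 to 48). The conclusion depends on there being no effective limit on ICOS-low entry, which the documents do not state, and on 28% applying to on-study fresh biopsies. At assumed prevalences of 20% to 50%, expected enrolment is 50 to 20. The totals of 120 and 498 are about 41 too low on account of the two gastric cohorts.

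A reader might infer more than this, and the documents do not support it:
- That 15 cannot be reached. It is very unlikely under the assumptions above, not impossible.
- That pre-screening is excluded. It is not required, and section 6.9 permits it.
- That 36 subjects are needed. Thirty-six is an average; at 36 the quota is met only 57% of the time.
- That the Part C total should be 120 − 30 + 71 = 161. That sum leaves the other quota cohorts (C01, C02, C06, C07) at 15, and the text available gives no prevalence from which to check them.

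SAP section 3.3.1 makes the Phase 2 efficacy analysis descriptive, so the consequence lies in planned size and exposure rather than in a power claim.

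**What to change.** Either of two changes resolves it.

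1. Keep the current rule. Restate the expected size of C04 and C64 as about 36 each (range about 24 to 48). Add to section 5.5 an over-enrolment sentence like the one in section 5.6, with a maximum number per cohort. Note beside the 120 and 498 that they are about 41 too low on account of the gastric cohorts alone. The same figures in the Synopsis, section 9.4.1 and SAP section 5 should follow.
2. Keep about 15 treated. State in section 5.5 the cap on ICOS-low enrolment that achieves this, when it applies relative to the screening biopsy, and how many patients are expected to be biopsied.

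Making archival ICOS screening a condition of entry is not offered as a remedy. The gastric quota counts fresh biopsies, and the documents give no agreement rate between archival and fresh scores from which to judge whether 15 would then be enough.

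The cost is a few restated figures and one or two sentences in an amendment. No analysis method changes.
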